5.2. Efficacy Analysis Population

Efficacy analysis population is not used since efficacy is not assessed in this survey.

5.3. Other Analysis Population

No analysis population other than safety analysis population is used in this survey.

5.4. Subgroup

Safety analysis by subgroup is to be performed for the following subject characteristics:

- Gender [male, female] (reference population: male).
- Hepatic dysfunction [no, yes] (reference population: no): Hepatic dysfunction is identified in accordance with separately prescribed “procedure for extracting hepatic or renal dysfunction”.
- Renal dysfunction [no, yes] (reference population: no): Renal dysfunction is identified in accordance with separately prescribed “procedure for extracting hepatic or renal dysfunction”.
- Age at the time of vaccination [≥ 65 , < 70 ; ≥ 70 , < 75 ; ≥ 75 , < 80 ; ≥ 80 , < 85 ; ≥ 85] (reference population: ≥ 65 , < 70).

Safety analysis by subgroup is to be performed for the following other characteristics:

- Immunocompromised complication [no, yes] (reference population: no): Complication is identified in accordance with separately prescribed “definition of ‘immunocompromised’ in P13 adults”.
- Simultaneous vaccination with other vaccine [no, yes] (reference population: no).
- More than once Prevenar13 vaccination [once, more than once] (reference population: once).

- Prior vaccination of polyvalent pneumococcal polysaccharide vaccines [no, 1 year ago from the day before Prevenar13 vaccination, 1-5 years ago, more than 5 year ago, unknown date] (reference population: no).
- Subjects ineligible for vaccination: Subject population ineligible for vaccination as described in the package insert. Criteria for subjects ineligible for vaccination is based on separately prescribed “procedure for extracting subjects ineligible for vaccination”. Reference population is not used since there is no category within the subgroup.

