6.1. Safety Specifications

- 1) Safety in persons with immunocompromised state
- 2) Safety of concurrent vaccination with other vaccines
- 3) Safety in the elderly (adults aged 65 years or older) who received multiple vaccinations with Prevenar 13
- 4) Safety of Prevenar 13 in the elderly (adults aged 65 years or older) with a history of immunization with polyvalent pneumococcal capsular polysaccharide vaccines

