7.5 Target Sample Size

7.5.1 Planned sample size of the investigation

600 persons (number of persons to be registered)

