7.5.2 Rationale

In the age group of 65 years or older in a clinical study, B1851088 (noninferiority study) involving elderly subjects (adults aged 65 years or older) without history of immunization with pneumococcal vaccines and a clinical study, 6115A1-3004 (open-label study) involving

adults aged 50 years or older conducted in Japan, the incidence of local reactions reported by the subjects using an electronic diary during 14 days after vaccination with Prevenar 13 was 55.8% and 63.6%, respectively, and the incidence of systemic reactions was 37.9% and 52.6%, respectively. In the two studies, the incidence of AEs (adverse reactions) related to Prevenar 13 reported by the investigators during approximately one month after vaccination with Prevenar 13 was 3.9% (13/333) and 6.6% (9/136), respectively. The results of comparison between Japanese and overseas clinical study data revealed no new risk factor requiring attention in the Japanese subjects aged 65 years or older. In the Japanese clinical studies, 518 elderly subjects aged 65 years or older (B1851088, n = 382; and 6115A1-3004, n = 136) received Prevenar 13, and 469 subjects included in the safety set (B1851088, n = 333; and 6115A1-3004, n = 136) were evaluated for safety. Consequently, for the safety of Prevenar 13 under actual use conditions after marketing, a planned sample size of the investigation was set to 600 persons to collect and examine safety information from a subject scale equivalent to those of the Japanese clinical studies.

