8.2.3.3. Subgroup Analysis

Number of vaccinees experiencing at least one adverse reaction and its proportion are to be calculated by subgroups as defined in [Section 5.4](#) (excluding subjects ineligible for vaccination). To assess the association between vaccinee characteristics and occurrence of adverse reactions, risk ratio and its 95% confidence interval are to be calculated as described in [Section 8.1.3](#).

To evaluate the safety in specific populations of vaccinees in detail, analyses are to be performed in the following subgroups.

- **Vaccinees with hepatic dysfunction, renal dysfunction and simultaneous vaccination with other vaccine**

Number of vaccinees experiencing adverse reactions and its proportion are to be calculated by SOC and PT in each subgroup.

- **Vaccinees with immunocompromised complication**

Number of vaccinees experiencing adverse reactions, local and systemic reactions and adverse events with its proportion are to be calculated by SOC and PT.

- **Vaccinees with prior vaccination of polyvalent pneumococcal polysaccharide vaccines**

Number of vaccinees experiencing adverse reactions, local and systemic reactions and adverse events with its proportion are to be calculated by SOC and PT by prior vaccination of polyvalent pneumococcal polysaccharide vaccines [1 year ago from the day before Prevenar13 vaccination, 1-5 years ago, more than 5 year ago, unknown date].

- **Vaccinees with immunocompromised complication and prior vaccination of polyvalent pneumococcal polysaccharide vaccines**

Number of vaccinees experiencing adverse reactions, local and systemic reactions with its proportion are to be calculated by SOC and PT by prior vaccination of polyvalent pneumococcal polysaccharide vaccines [1 year ago from the day before Prevenar13 vaccination, 1-5 years ago, more than 5 year ago, unknown date].

- **Subjects ineligible for vaccination**

Reports described below are to be prepared for subjects ineligible for vaccination (See [Section 5.4](#)) and used as a reference for reporting safety information of these subjects. If there are less than 10 subjects ineligible for vaccination, however, safety information of these subjects are to be reported with a listing of vaccinees and other forms, and reports described below are not to be prepared.

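### The SAP pre-specifies no pooled any-versus-none estimate for prior polysaccharide vaccination (safety specification 4); only four separate levels are compared with none

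*SAP*

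**What the plan says.** Protocol 6.1 names four safety specifications. The fourth is "Safety of Prevenar 13 in the elderly (adults aged 65 years or older) with a history of immunization with polyvalent pneumococcal capsular polysaccharide vaccines". It gives no interval since that immunization and states no comparison group.

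SAP 5.4 gives the other three specifications two levels each: immunocompromised complication (no, yes), simultaneous vaccination (no, yes) and number of Prevenar 13 vaccinations (once, more than once). For prior polysaccharide vaccination the levels are "no, 1 year ago from the day before Prevenar13 vaccination, 1-5 years ago, more than 5 year ago, unknown date] (reference population: no". SAP 8.2.2 uses the same levels for the baseline table.

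SAP 8.2.3.3 plans, for each level, the number and proportion of vaccinees with at least one adverse reaction, and a risk ratio with 95% interval against the reference. Under "Vaccinees with prior vaccination of polyvalent pneumococcal polysaccharide vaccines" it also plans tables by System Organ Class and Preferred Term of adverse reactions, local and systemic reactions, and adverse events. These are split by the same four levels of prior vaccination. The tables for immunocompromised vaccinees with prior vaccination use that split too.

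Two other provisions bear on the point. SAP 9 plans one undivided listing of prior-vaccinated persons who had adverse reactions. SAP 8.2.3.4 allows additional exploratory analyses.

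**The concern.** The specification concerns anyone with this history. The plan answers it with four ratios, and one of them is for people whose vaccination date is unknown. Those people cannot inform a question about interval, but they contribute fully to a question about any prior vaccination. If reactions are as infrequent as the investigator-reported rates in the cited studies, each ratio would rest on very few events and could be undefined on the log scale. The single estimate that uses all prior-vaccinated persons, with its interval and its row in the risk-ratio chart of SAP 10.1, is not among the planned outputs.

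**Working it through.** **Inputs from the documents.** Planned size: "600 persons (number of persons to be registered" (Protocol 7.5.1). The investigator-reported adverse reaction rate "was 3.9% (13/333) and 6.6% (9/136), respectively" (Protocol 7.5.2). Check: 13/333 = 3.9%, 9/136 = 6.6%, 333 + 136 = 469, and pooled (13 + 9)/469 = 22/469 = 4.7%. Diary-reported local reactions were 55.8% and 63.6%, and systemic reactions 37.9% and 52.6% (Protocol 7.5.2). The size of 600 comes from no formula. It was chosen "to collect and examine safety information from a subject scale equivalent to those of the Japanese clinical studies", so there is no precision target to reproduce.

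**Assumptions, not in the documents.** Share with prior polysaccharide vaccine: 10%, 25% or 40% of 600. Prior-vaccinated persons split equally over the four levels. Same true risk p in all groups (risk ratio 1).

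**Formulas.** SE of the log risk ratio = sqrt[(1−p)/(n1·p) + (1−p)/(n0·p)], where n1 is the prior-vaccine group or one stratum and n0 is the group with none. The 95% limits are exp(±1.96·SE), so the upper-to-lower limit ratio is exp(3.92·SE). The chance of no events in a stratum of size n is (1−p)^n.

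**Results at p = 0.047:**

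| Share | n0 | Any prior: n, expected events | SE | 95% limits | Limit ratio | One stratum: n, expected events | SE | 95% limits | Limit ratio |
|---|---|---|---|---|---|---|---|---|---|
| 10% | 540 | 60, 2.8 | 0.613 | 0.30–3.3 | 11 | 15, 0.7 | 1.179 | 0.10–10.1 | 102 |
| 25% | 450 | 150, 7.1 | 0.425 | 0.44–2.3 | 5.3 | 37.5, 1.8 | 0.765 | 0.22–4.5 | 20 |
| 40% | 360 | 240, 11.3 | 0.375 | 0.48–2.1 | 4.4 | 60, 2.8 | 0.628 | 0.29–3.4 | 12 |

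With so few events the large-sample formula is rough, so the stratum figures show scale only.

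**Empty strata.** At a 25% share, 0.953^37.5 = 0.16 for a given stratum, and 1 − (1 − 0.164)^4 = 0.51 for at least one of the four. For a given stratum the chance is 49% at a 10% share and 6% at 40%. A stratum with no events has a risk ratio of 0 and no log-scale interval. SAP 8.1.3 names an exact method for the proportion but no interval method for the risk ratio.

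**Results at p = 0.5, 25% share.** Pooled: SE = sqrt(1/150 + 1/450) = 0.094, limit ratio exp(3.92 × 0.094) = 1.45. One stratum: SE = sqrt(1/37.5 + 1/450) = 0.170, limit ratio 1.95.

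**The case against.** A reader might infer that specification 4 gets no usable estimate. The documents do not support that. The four levels are mutually exclusive, and SAP 8.2.3.3 plans counts and proportions at every level, including none. The pooled risk ratio follows by adding four planned numerators and four planned denominators. What is absent is a pre-specified output, not the information.

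It is also tempting to call the strata thin as a matter of fact. Neither document gives the number with prior vaccination or how it divides. The 4.7% rate may also be too low for this survey. Protocol 7.2.6 feeds a Day 0 to Day 13 diary into the collection of adverse events by interview, and SAP 10.2 defines local and systemic reactions as kinds of adverse reaction. At diary-like rates the strata work.

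The protocol does not ask for a comparison with none; the SAP chose that reference. The survey is descriptive, with no significance level or decision rule (SAP 4). Nor is the lack of a none column in the detailed tables a fault peculiar to this specification: the SAP's other special-population tables also show only the affected group.

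All of this stands, and it limits the weight of the point. Two counter-arguments do not remove it. The listing in SAP 9 covers only persons who had reactions, so it has no denominator and gives no incidence. Under SAP 8.2.3.4, exploratory results are reported only if they help interpretation materially, so an unremarkable pooled result could go unreported. Since the SAP already plans risk ratios with intervals for this variable, the request is for estimation and needs no testing framework.

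**Conclusion.** The gap is real but minor. Specification 4 is the only one of the four without a two-level contrast, and no planned output gives the pooled ratio, its interval or a chart row. At 4.7%, equal strata and a 10% to 40% share, pooling narrows the limit ratio from about 102–12 to about 11–4.4. At a rate near 50% and a 25% share the gain is small, from 1.95 to 1.45. Both the share and the equal split are assumptions.

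Pooling does not make the estimate precise at low rates: at 4.7% and a 25% share the limits are still 0.44 to 2.3. The benefit is that the stated question gets one planned answer using all prior-vaccinated persons, including those with unknown dates.

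**What to change.** - **SAP 5.4:** add a contrast for prior polyvalent polysaccharide vaccine with levels [no, any], reference no. Report its proportion, risk ratio, 95% interval and a row in the risk-ratio chart. Keep the three intervals and unknown date as a secondary breakdown.
- **SAP 8.2.3.3:** add a total column for any prior vaccination to the prior-vaccine tables. A none column is optional, since the comparable tables for other special populations have none.

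The cost is SAP wording, one extra row in the subgroup analysis and chart, and one extra column per table. No new data are needed.

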6. ENDPOINTS AND COVARIATES

6.1. Safety Endpoints

- Adverse reaction: Adverse event whose causal relationship is confirmed by investigator or sponsor.
- Adverse event: Adverse event regardless of causal relationship.
- Priority survey items: No priority survey items in this survey.

6.2. Efficacy Endpoints

Efficacy is not assessed in this survey.

6.3. Other Endpoints

No endpoint other than safety endpoint is used in this survey.

6.4. Covariate

There is no covariate identified from previous clinical study data, etc. or potential covariate in terms of the safety of Prevenar13.

7. HANDLING OF MISSING DATA

When seriousness, corrective treatment and outcome of adverse events are missing, these data are handled as “unknown” for counting.

Since laboratory testing is not mandatory in this survey, laboratory test value or date of measurement is not imputed.

Data not yet cleaned are to be handled as follows:

- Missing data: Handled as missing both in the counting and listing (category variable classified as “unknown”).
- Inconsistent data: Handled as missing both in the counting and listing. However, a list of handling data is separately prepared.

- No signature: Data included in the CRF without a signature of contracting investigator (including CRF with a signature of person other than contracting investigator only) are to be handled as missing both in the counting and listing.

8. STATISTICAL METHOD AND STATISTICAL ANALYSIS

8.1. Statistical Method

8.1.1. Analysis of Continuous Data

Summary statistics (number of vaccinees, mean, standard deviation, median, maximum and minimum) are to be calculated.

8.1.2. Analysis of Categorical Data

Frequency (number of vaccinees) and its proportion of each category are to be calculated.

8.1.3. Analysis of Binary Data

Frequency and its proportion are to be calculated. Two-sided 95% confidence interval (exact method) is to be calculated for obtaining the confidence interval of the proportion.

To compare the proportion between subgroups, risk ratio and its 95% confidence interval are to be calculated. In addition, risk ratio and its 95% confidence interval are to be shown in the figure (See [Section 10.1](#)).

Statistical hypothesis testing is not to be formally performed in this survey. If statistical hypothesis testing becomes necessary, Fisher's exact test is to be performed for association with nominal scale data, Cochran-Armitage test (exact method) for association with ordinal scale data.

8.2. Statistical Analysis

8.2.1. Summary of Vaccinees

- **Number of institutions and vaccinees to be surveyed by establishment category**

Number of institutions and vaccinees with their proportion by establishment category are to be calculated for the vaccinees whose CRFs collected:

- National, public and private university hospital;
- National hospital established by MHLW;
- Prefectural and municipal hospital;
- Public institution;
- Hospital established by corporations and individuals not described above;
- Private practice/clinic.

Additionally, mean, minimum and maximum of the number of vaccinees per institution are to be calculated.

- **Disposition of vaccinees**

Numbers of vaccinees are to be calculated by those registered, those who completed the survey and those included in the safety analysis population. Also, number of vaccinees are to be calculated by those whose CRFs not collected and those excluded from the safety analysis population as well as by reason for exclusion.

- **Listing of discontinuation and withdrawal**

Numbers of subjects who discontinued vaccination and its proportion are to be calculated in the safety analysis population as well as by reason for exclusion.

- **Listing of subjects excluded from safety analysis population**

Listing of subjects excluded from safety analysis population and the reason for exclusion is to be prepared.

8.2.2. Characteristics and Treatment History of Vaccinees

- **Vaccinee characteristics**

The following characteristics are to be calculated in the safety analysis population in accordance with [Section 8.1](#):

- Gender [male, female];
- Age (continuous);
- Age [<65; ≥65, <70; ≥70, <75; ≥75, <80; ≥80, <85; ≥85];
- Inpatient/outpatient status at the time of initial vaccination [inpatient, outpatient];
- Weight [<40 kg; ≥40 kg, <50 kg; ≥50 kg, <60 kg; ≥60 kg, <70 kg; ≥70 kg, <80 kg; ≥80 kg];
- Complication [no, yes];
- Immunocompromised complication [no, yes]: See [Section 5.4](#) for definition of immunocompromised complication;
- Hepatic dysfunction [no, yes]: See [Section 5.4](#) for definition of hepatic dysfunction;
- Renal dysfunction [no, yes]: See [Section 5.4](#) for definition of renal dysfunction;
- More than once Prevenar13 vaccination [once, more than once];

- Simultaneous vaccination with other vaccine [no, yes];
- Prior vaccination of polyvalent pneumococcal polysaccharide vaccines [no, 1 year ago from the day before Prevenar13 vaccination, 1-5 years ago, more than 5 year ago, unknown date].

The following number of vaccinees and its proportion are to be calculated by System Organ Class (SOC) and Preferred Term (PT) in the safety analysis population:

- Disposition of medical history;
- Disposition of complication.

The following number of vaccinees and its proportion are to be calculated in the safety analysis population:

- Disposition of vaccines before Prevenar13 vaccination;
- Disposition of vaccines after Prevenar13 vaccination.
- **Prevenar13 vaccination data**

The following Prevenar13 vaccination data are to be collected in the safety analysis population:

- Dose [0.5 ml, other];
- Location [upper arm, other];
- Route [intramuscular, other];
- Body temperature at the time of vaccination [$<37.5^{\circ}\text{C}$, $\geq 37.5^{\circ}\text{C}$, not measured].
- **Simultaneous vaccination data**

Simultaneous vaccination data are to be collected in the safety analysis population:

- Name of vaccine simultaneously administered [Prevenar13 alone, name of vaccine simultaneously administered];
- Location [Prevenar13 alone, location of simultaneous vaccination].

8.2.3. Safety Analysis

8.2.3.1. Adverse Reaction

- **All adverse reaction**

Number of vaccinees experiencing adverse reactions and its proportion are to be calculated. Number of vaccinees experiencing adverse reactions and its proportion are also to be calculated by SOC and PT.

Number of adverse reactions is to be calculated. However, the same adverse reaction which occurred more than once in the same vaccinee is to be calculated as 1 adverse reaction.

- **Serious adverse reaction**

Number of vaccinees experiencing serious adverse reactions and its proportion are to be calculated by SOC and PT.

- **Details of adverse reaction**

Number of vaccinees experiencing adverse reactions and its proportion are to be calculated by SOC and PT for the following data:

- Seriousness [serious, non-serious];
- Expected/unexpected [expected, unexpected];
- Corrective treatment [yes, no];
- Outcome [not recovered, recovered with sequelae, recovering, resolved/recovered, unknown];
- Severity [mild, moderate, severe].

If the same adverse reaction (the same PT) occurred more than once in the same vaccinee, number of vaccinees experiencing the adverse reactions is to be calculated as follows:

- Seriousness: Serious if both serious and non-serious reactions occurred;
- Expected/unexpected: Unexpected if both expected and unexpected reactions occurred;
- Number of days to onset: Number of days to onset of the first reaction;
- Corrective treatment: Yes if vaccinees experienced both reactions requiring and not requiring treatment;
- Outcome: Outcome of the reaction lastly occurred in the vaccinee;

- **Severity:** If the vaccinee experienced reactions with more than one severity, select one in the following order of priority: severe, moderate and mild.

- **Timing of onset of adverse reaction**

Number of vaccinees experiencing adverse reactions and its proportion are to be calculated by timing of initial onset [Day 0, Day 1, Day 2, Day 3, Day 4, Day 5, Day 6, Days 7-27, on or after Day 28] by SOC and PT. Proportion of vaccinees experiencing adverse reactions is to be calculated as the proportion to total number of vaccinees included in the safety analysis population for all the timing of onset.

- **Occurrence of adverse reactions by inclusion of/exclusion from safety analysis population**

For the vaccinees whose CRFs collected, a listing of adverse reactions in the vaccinees excluded from safety analysis population is to be prepared. Additionally, number of vaccinees experiencing adverse reactions is to be calculated by inclusion of/exclusion from safety analysis population by SOC and PT.

- **Local reaction**

Number of vaccinees experiencing local reactions and its proportion are to be calculated by SOC and PT. See [Section 10.2.1](#) for definition of local reaction.

- **Systemic reaction**

Number of vaccinees experiencing systemic reactions and its proportion are to be calculated by SOC and PT. See [Section 10.2.2](#) for definition of systemic reaction.

- **Pyrexia**

Number of vaccinees experiencing pyrexia and its proportion are to be calculated by presence or absence of immunocompromised complication and simultaneous vaccination with other vaccine. See [Section 10.2.3](#) for definition of pyrexia.

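### When the same reaction recurs, the SAP's last-episode outcome rule can drop an earlier unfavourable outcome from the outcome counts

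*SAP*

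**What the plan says.** SAP 8.2.3.1, under Details of adverse reaction, asks for the number and proportion of vaccinees by SOC and PT for seriousness, expectedness, corrective treatment, outcome and severity. The outcome categories are "Outcome [not recovered, recovered with sequelae, recovering, resolved/recovered, unknown".

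The merging rules apply under this condition: "If the same adverse reaction (the same PT) occurred more than once in the same vaccinee". They are:

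- "Seriousness: Serious if both serious and non-serious reactions occurred"
- "Expected/unexpected: Unexpected if both expected and unexpected reactions occurred"
- "Corrective treatment: Yes if vaccinees experienced both reactions requiring and not requiring treatment"
- for severity, "select one in the following order of priority: severe, moderate and mild"
- "Outcome: Outcome of the reaction lastly occurred in the vaccinee"

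Days to onset takes the first episode. The SAP gives no reason for handling outcome differently from the four worst-case items.

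SAP 7 adds a rule for gaps: "When seriousness, corrective treatment and outcome of adverse events are missing, these data are handled as" *unknown*. Nothing in SAP 7 or 8.2.3.1 carries an earlier known outcome forward when the last one is missing.

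**The concern.** Seriousness, expectedness, treatment and severity are each resolved so that the worse report survives the merging. Outcome, the item that records lasting harm, is resolved by calendar order. If the first episode left sequelae and a later episode of the same PT cleared, the vaccinee is counted under *resolved/recovered* and adds nothing to *recovered with sequelae*. If the later episode's outcome was not reported, the vaccinee is counted under *unknown*, although an unfavourable outcome is on file.

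At stake is the count of vaccinees left with sequelae or not recovered, in data that Protocol section 5 says will support the reexamination application. Such outcomes are likely to be rare, so losing even one could turn a count of one into zero.

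**Working it through.** The plan has no figure of its own to reproduce here. The check applies the rules to the possible cases.

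**1. A worked pair.** Two episodes of one PT in one vaccinee:

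| Item | Episode 1 | Episode 2 | Rule | Tabulated |
|---|---|---|---|---|
| Seriousness | serious | non-serious | worst | serious |
| Severity | severe | mild | worst | severe |
| Outcome | recovered with sequelae | resolved/recovered | last | resolved/recovered |

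The sequelae category gets no count. With a missing outcome for episode 2, the last line becomes *unknown*.

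**2. All outcome pairs.** Five categories give 5 × 5 = 25 ordered pairs (earlier, last). The vaccinee leaves both unfavourable categories when the earlier outcome is *recovered with sequelae* or *not recovered* and the last is *resolved/recovered*, *unknown* or *recovering*: 2 × 3 = 6 pairs. In 2 × 2 = 4 of these the last is *resolved/recovered* or *unknown*. Under any strict ranking of the five categories, the last outcome ranks better than the earlier one in 5 × 4 / 2 = 10 pairs. These are counts of logical cases, not expected frequencies.

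**3. Direction.** A last episode in one of the two unfavourable categories is itself an episode in one of them. So the number counted under the last-episode rule cannot exceed the number with any such episode. It can only be equal or lower.

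**4. Does the same information appear elsewhere?**

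- The adverse-event tables (SAP 8.2.3.2) and the subgroup analyses (8.2.3.3) have no outcome breakdown.
- SAP 9 plans listings of vaccinees with adverse reactions and with serious adverse reactions, but does not state their columns.
- Outcome is a named column only in the listing of subjects ineligible for vaccination, which is prepared only if there are at least 10 of them.

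**5. How many vaccinees could be affected?** The documents give no recurrence rate, so only the pool from which cases would come can be sketched. The assumption is that the earlier Japanese studies' rates (Protocol 7.5.2) apply to all 600 registered.

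- Investigator-reported reactions: 600 × 13/333 = 23.4 and 600 × 9/136 = 39.7, so about 23 to 40 vaccinees with any reaction.
- If the survey's diary raised reporting to the e-diary rates for local reactions: 600 × 0.558 = 334.8 and 600 × 0.636 = 381.6, so about 335 to 382.

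Affected vaccinees are the part of that pool with the same PT twice in about 28 days and with an unfavourable earlier outcome. The documents do not allow that part to be estimated.

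**The case against.** **Last status is a recognised convention.** Outcome is a status, and reporting the latest one is defensible when pre-specified. This stands in part. But the last episode's outcome is not necessarily the vaccinee's final status, because a sequela of the first episode need not vanish when the second resolves. Protocol 9.3 itself has related events followed until the event or its sequela resolves or is acceptably stable.

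**The scenario is narrow.** Protocol 7.3.7 has outcomes monitored, as a rule, until symptoms resolve. A *not recovered* episode followed by a separate new episode of the same PT fits poorly with that. This stands: the plausible case is mainly sequelae followed by a resolved or unreported recurrence.

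**The listings may show it.** They may, but the SAP does not say so, and a listing does not correct a table.

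**Any ranking is a judgement.** This stands. The documents give no order, and it is arguable whether *recovered with sequelae* or *not recovered* is worse. The sponsor should choose.

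Three stronger readings are tempting but unsupported:

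- A reader might infer that a table will show a reaction as both serious and resolved. No seriousness-by-outcome cross-table is specified, and each item is counted separately. The point rests on the outcome counts alone.
- A reader might infer that the rule is wrong because the merged record can match neither episode. With 2 × 3 × 5 = 30 episode types there are 900 ordered pairs. Under the current rule the record equals the last episode in 3 × 6 × 25 = 450 pairs, the earlier one in 3 × 6 × 5 = 90, and both in 30. That leaves 900 − (450 + 90 − 30) = 390 mixed records. Under a worst-outcome rule it equals each episode in 3 × 6 × 15 = 270 pairs and both in 30, leaving 900 − (270 + 270 − 30) = 390. The change does not cure this, so it is no argument for the change.
- A reader might infer that everyone whose worst episode came first is misclassified. If a severe first episode and a mild second one both resolved, the outcome shown is the same under either rule.

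**Conclusion.** The point holds in a limited form. For recurrent PTs, the outcome rule can remove a known *recovered with sequelae* or *not recovered* from the counts, and for these two categories combined the error runs only towards fewer. That follows from the text of SAP 8.2.3.1 and SAP 7 and needs no numerical assumption.

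The size is unknown and probably small. Recurrence of the same PT after one vaccination within about 28 days, with a worse earlier outcome, should be uncommon, but this is a judgement and not a figure from the documents. No proportionate effect on any PT row can be stated. The primary endpoint in Protocol 7.7, the incidence of adverse reactions, is unchanged, because a vaccinee with a recurrent reaction counts once whatever the outcome. The point is worth acting on because the correction costs little.

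**What to change.** Make one of two changes to SAP 8.2.3.1:

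1. Replace the outcome rule with: the worst known outcome over all episodes of the PT in the vaccinee, in an order that the sponsor states before the tables are run. A missing outcome never replaces a known unfavourable one. The sponsor should also state how a resolved episode combined with a missing one is shown.
2. Keep the last-episode rule and add, by PT, the number of vaccinees with any episode *recovered with sequelae* or *not recovered*. This needs no ranking.

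With either change, state in SAP 9 that the adverse-reaction listing shows each episode's own outcome.

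The cost is a sentence or two in the SAP and a small programming change. No new data are needed, since Protocol 7.3.7 already has outcome recorded for adverse events. The downside is that under the first option the table shows the worst rather than the latest episode's outcome, while the listing still gives the latest. Under the second, the table gains one extra row.
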